6.2.2. Hepatotoxicity Stopping Rules

Patients with abnormal hepatic laboratory values (ie, ALP, AST, ALT, total bilirubin TBL) and/or international normalized ratio (INR) and/or signs/symptoms of hepatitis may meet the criteria for withholding or permanent discontinuation of ABI-009 as specified in the Guidance for Industry Drug-Induced Liver Injury: Premarketing Clinical Evaluation, July 2009.

6.2.2.1. Criteria for Permanent Discontinuation of ABI-009 Due to Potential Hepatotoxicity

ABI-009 should be discontinued permanently and the patient should be followed for possible drug-induced liver injury (DILI), if **ALL** of the criteria below are met:

- TBL > 2x upper limit of normal (ULN) or INR > 1.5x
- AND increased AST or ALT from the relevant baseline value as specified below:

Baseline AST or ALT value	AST or ALT elevation
< ULN	≥ 3x ULN

- AND no other cause for the combination of the above laboratory abnormalities is immediately apparent; important alternative causes for elevated AST/ALT and/or TBL values include, but are not limited to:
 - Hepatobiliary tract disease
 - Viral hepatitis (eg, Hepatitis A/B/C/D/E, Epstein-Barr Virus, Cytomegalovirus, Herpes Simplex Virus, Varicella, Toxoplasmosis, and Parvovirus)
 - Right sided heart failure, hypotension or any cause of hypoxia to the liver causing ischemia.
 - Exposure to hepatotoxic agents/drugs or hepatotoxins, including herbal and dietary supplements, plants and mushrooms
 - Heritable disorders causing impaired glucuronidation (eg, Gilbert's Syndrome, Crigler-Najjar syndrome) and drugs that inhibit bilirubin glucuronidation (eg, indinavir, atazanavir)
 - Alpha-one antitrypsin deficiency
 - Alcoholic hepatitis
 - Autoimmune hepatitis
 - Wilson's disease and hemochromatosis
 - Nonalcoholic Fatty Liver Disease including Steatohepatitis (NASH)
 - Non-hepatic causes (eg, rhabdomylosis, hemolysis)

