3.2. Inclusion Criteria

A patient will be eligible for inclusion in this study only if all of the following criteria are met:

1. Patients must have a histologically confirmed diagnosis of Ewing's sarcoma, PEComa, epithelioid sarcoma, desmoid tumor, chordoma, non-small cell lung cancer, small cell lung cancer, urethelial carcinoma, melanoma, renal cell carcinoma, squamous cell carcinoma of head and neck, hepatocellular carcinoma, classical Hodgkin's lymphoma, MSI-H/dMMR metastatic colorectal cancer, and tumors with genetic mutations sensitive to mTOR inhibitors, that is either metastatic or locally advanced and for which surgery is not a recommended option.
2. Patients must have one or more measurable target lesions by CT scan or MRI. Measurable disease by RECIST v1.1, confirmed by investigator.
3. Previously treated patient with Ewing's sarcoma, PEComa, epithelioid sarcoma, desmoid tumor, chordoma, non-small cell lung cancer, small cell lung cancer, urethelial carcinoma, melanoma, renal cell carcinoma, squamous cell carcinoma of head and neck, hepatocellular carcinoma, classical Hodgkin's lymphoma, MSI-H/dMMR metastatic colorectal cancer, and tumors with genetic mutations sensitive to mTOR inhibitors, if treatment is completed after 5 half-lives or ≥ 28 days prior to enrollment, whichever is shorter.
4. Eligible patients, 12-17 years (≥ 40 kg) or 18 years old or older, with Eastern Cooperative Oncology Group (ECOG) performance status 0 or 1.
5. Patients must have the following blood chemistry levels at screening (obtained ≤ 14 days prior to enrollment (local laboratory):
 - a. total bilirubin $\leq 1.5 \times$ upper limit of normal (ULN) mg/dl

- b. AST/ALT $\leq 2.5 \times$ ULN ($\leq 5 \times$ ULN if attributable to liver metastases); alk phos $< 3 \times$ ULN (patients with alk phos > 3 ULN will be allowed if due to bone metastases) AST $\leq 2.5 \times$ ULN ($\leq 5 \times$ ULN if attributable to liver metastases)
- c. serum creatinine $\leq 1.5 \times$ ULN

6. Adequate biological parameters as demonstrated by the following blood counts at screening (obtained ≤ 14 days prior to enrollment, local laboratory):

- a. Absolute neutrophil count (ANC) $\geq 1.5 \times 10^9/L$; b. Platelet count $\geq 100,000/mm^3$ ($100 \times 10^9/L$); c. Hemoglobin ≥ 9 g/dL.

7. Serum triglyceride < 300 mg/dL; serum cholesterol < 350 mg/dL.

8. Male or non-pregnant and non-breast feeding female:

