In the event of clinically significant AE in any part of the study, treatment may be withheld and supportive therapy administered as clinically indicated. If the toxicity or event is not grade 3/4 and resolves to baseline or grade 1 in less than or equal to 14 days of stopping therapy, then treatment may be restarted. Dose reduction of ABI-009 should be considered as clinically indicated.

If the toxicity does not resolve to at least grade 1 in less than 14 days, withdrawal from treatment with the IP is recommended. However, if the investigator and AADI Medical Monitor agree that further treatment would benefit the patient, treatment can continue with at least one dose level dose reduction, per Table 4.

Table 4. Dose Level Reduction Guidelines

Dose level	ABI-009 Dose/Schedule
1	Initial Dose: 56 mg/m ²
-1 (first dose reduction)	45 mg/m ²
-2 (second dose reduction)	30 mg/m ²

If an AE resolves to grade 1 or baseline at the reduced dose level, and no additional toxicities are seen during the following cycle of study treatment at the reduced dose, the dose may be increased to the previous dose level.

Any patient meeting the criteria for Hy's Law case (i.e. severe drug-induced liver injury) will be considered a dose-limiting toxicity. A Hy's Law case is defined as: AST or ALT values of $\geq 3 \times$ ULN AND with serum total bilirubin level (TBL) of $> 2 \times$ ULN without signs of cholestasis and with no other clear alternative reason to explain the observed liver-related laboratory abnormalities.

ABI-009 dose modification guidelines are outlined in Table 4 and Table 5

for clinically significant toxicities that are deemed related. The dosing schedule is described in the Schedule of Assessments, Table 2.

Table 5. Dose Modification Algorithms for Adverse Events Possibly Related to ABI-009

System/Organ	Adverse Event	CTCAE Grade v4.03	Dose modification Algorithm
Mucosa	Stomatitis, mucosal inflammation	Grade 2	Hold ABI-009 until resolution to Grade 1 or baseline and restart at the same dose for 1 st occurrence; for subsequent occurrences, drug will be restarted at a reduced dose; provide supportive care as clinically indicated.
		Grade ≥3	Hold ABI-009 until resolution to Grade 1 or baseline and restart at the same dose for 1 st occurrence for subsequent occurrences, drug will be restarted at a reduced dose; provide supportive care as clinically indicated.

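### The permanent ABI-009 liver stop in section 6.2.2.1 has no AST/ALT threshold for raised baselines, so some unexplained Hy's Law cases meet only the general Grade 3 hold or no hold criterion

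*Combined protocol and SAP*

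**What the plan says.** **Permanent stop (6.2.2.1).** The text is "ABI-009 should be discontinued permanently and the patient should be followed for possible drug-induced liver injury (DILI", provided that three things hold together: bilirubin (TBL) above 2x ULN or INR above 1.5x; an enzyme rise; and no other cause immediately apparent. The enzyme limb reads "AND increased AST or ALT from the relevant baseline value as specified below". The table beneath it has a single row: baseline below ULN, on-study value at least 3x ULN. Section 6.2.2.3 bars rechallenge for patients who clearly meet the permanent-stop criteria.

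**Eligibility (3.2, criterion 5).** AST/ALT may be up to 2.5x ULN, or up to 5x "if attributable to liver metastases". TBL may be up to 1.5x ULN.

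**Conditional hold (6.2.2.2).** At any baseline, ABI-009 is to be withheld for AST/ALT above 8x ULN; above 5x but below 8x for two weeks or more, or when enhanced monitoring cannot be kept; at least 3x with signs or symptoms of hepatitis; TBL above 3x; or ALP above 8x. Rechallenge may be considered if an alternative cause is found and values return to normal or baseline. Section 6.2.2.3 adds unanimous agreement of patient, investigator and medical monitor.

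**General rules (6.2.1).** Grade 3 non-hematologic toxicity holds both drugs until Grade 1 or less, after which the ABI-009 dose is modified. For any clinically significant adverse event, "treatment may be withheld and supportive therapy administered as clinically indicated". If an event below Grade 3 "resolves to baseline or grade 1 in less than or equal to 14 days of stopping therapy, then treatment may be restarted". Otherwise "withdrawal from treatment with the IP is recommended", but if investigator and medical monitor agree, "treatment can continue with at least one dose level dose reduction". Separately, any Hy's "Law case (i.e. severe drug-induced liver injury) will be considered a dose-limiting toxicity". That case is defined by AST or ALT at least 3x and TBL above 2x ULN, without cholestasis or another clear explanation. Baseline plays no part in it, and no ABI-009 action is attached.

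**The concern.** The permanent stop needs every limb, and the enzyme limb is keyed to a baseline category that some eligible patients do not fall in. For a patient who enters with both AST and ALT at or above ULN, no on-study value can satisfy it, and the rechallenge ban that depends on it falls away too.

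At stake is consistent handling of the pattern that the protocol itself labels severe drug-induced liver injury. The same on-study values, with the same absence of symptoms or explanation, end ABI-009 for good in a patient who entered at 0.9x ULN. In a patient who entered at 1.5x ULN they may lead only to a hold that ends when the grade falls, or to a decision left to the investigator. Criterion 5a caps entry TBL at 1.5x ULN, so TBL above 2x is a rise during the study even when the enzymes were raised at entry.

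**Working it through.** The protocol gives no figure to reproduce; this is a check of which rules are met.

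**Inputs.** The rules of 6.2.1, 6.2.2.1 and 6.2.2.2 as set out above, with all values as multiples of ULN. One input is an assumption: Grade 3 is taken as AST/ALT above 5x or TBL above 3x. It is read from 6.3.1, which lists AST/ALT above 3x and up to 5x, or TBL above 1.5x and up to 3x, for withholding nivolumab. That section withholds at Grade 2 and stops permanently at Grade 3 or 4.

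**Case examined.** AST equal to ALT, no symptoms, no other cause, no cholestasis, ALP at most 8x, INR at most 1.5x, under two weeks' duration, monitoring kept.

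**Step 1: permanent stop.** Stop = (TBL > 2 or INR > 1.5) and (baseline < 1 and on-study enzyme ≥ 3) and (no other cause). With both baselines at 1 or more, the middle term is false for every on-study value, so the stop is never met. Testing up to AST/ALT 30x and TBL 10x confirmed this.

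**Step 2: what applies instead.** Take baseline 1.5 for both enzymes, AST/ALT from 3.0 to 20.0 by 0.1 (171 values) and TBL from 2.1 to 10.0 by 0.1 (80 values). That gives 171 × 80 = 13,680 Hy's Law combinations.

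- TBL above 3x, so 6.2.2.2 hold: 171 × 70 = 11,970.
- TBL at most 3x but AST/ALT above 8x, so 6.2.2.2 hold: 120 × 10 = 1,200.
- Sum under a 6.2.2.2 hold: 13,170, and 13,170 / 13,680 = 96%.
- AST/ALT 5.1 to 8.0, TBL 2.1 to 3.0, so general Grade 3 hold only: 30 × 10 = 300.
- AST/ALT 3.0 to 5.0, TBL 2.1 to 3.0, so no hold criterion met: 21 × 10 = 210.
- Check: 13,170 + 300 + 210 = 13,680.

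These counts map the rules. They are not patient frequencies.

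**Step 3: side by side.**

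| On-study AST/ALT, TBL | Both baselines 0.9x | Both baselines 1.5x |
|---|---|---|
| 4.5x, 2.5x | Permanent stop | DLT; no stop, no hold criterion |
| 6.0x, 2.5x | Permanent stop | Grade 3 hold only |
| 4.5x, 3.1x | Permanent stop | 6.2.2.2 hold and Grade 3 hold |
| 12x, 6x | Permanent stop | 6.2.2.2 hold and Grade 3 hold |

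Baselines of 1.0x and 2.5x give the same results as 1.5x.

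**Step 4: is the lower window robust?** A second enumeration took 16 pairs of raised baselines, 25 AST/ALT pairs from 3x to 5x, three TBL values above 2x and up to 3x, and three ALP values up to 8x: 16 × 25 × 3 × 3 = 3,600 combinations. Permanent stop 0, 6.2.2.2 hold 0, Grade 3 hold 0, Hy's Law DLT 3,600. If symptoms are present, the 6.2.2.2 hold is met in all 3,600, so the absence of symptoms is essential. With one or both enzymes normal at entry, the stop was met in 225 of 225.

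**Step 5: mixed baselines.** Both table columns say AST or ALT without tying them to one enzyme. Suppose AST goes from 1.5x to 4.5x and ALT from 0.9x to 2.0x, with TBL 2.5x. Read per enzyme, the stop is not met; read literally, it is. The text does not settle which.

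**The case against.** A reader might infer that patients with raised baselines have no stopping protection for ABI-009. The documents do not support that. Section 6.2.2.2 expressly covers patients with abnormal baseline transaminases and applies at any baseline. Its restart condition requires an alternative cause, so an unexplained case held under it has no stated way back and is in practice stopped. That covers TBL above 3x, AST/ALT above 8x, and AST/ALT between 5x and 8x that lasts two weeks or cannot be monitored. Holding and investigating is also a defensible design when a raised baseline clouds attribution. Below those levels, 6.2.1 still permits a hold and recommends withdrawal if the event is unresolved at 14 days. Nivolumab is withheld if the event is judged immune-mediated (6.3.1), and drug-induced liver injury is a named example of a possible SAE (9.4.1).

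Two further objections have weight. First, 6.2.1 calls a Hy's Law case severe, and 6.3.1 pairs that word with Grade 3. A site that graded on that basis would apply the Grade 3 hold, and the window with no hold criterion would close. Second, 6.2.2 refers to the July 2009 FDA guidance on drug-induced liver injury, which cannot be checked here. A table row may also have been lost in extraction, although the row shown is complete and the neighboring 6.2.2.2 table came through intact.

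What stands is narrower. The permanent stop as written cannot be met from a raised baseline. In the TBL range above 2x and up to 3x, neither the general Grade 3 hold nor the discretionary rule carries the alternative-cause condition.

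**Conclusion.** The point holds as a gap in a safety rule, of moderate weight. Patients with both AST and ALT at or above ULN at entry cannot meet the 6.2.2.1 stop or the rechallenge ban tied to it. The practical consequence is confined to asymptomatic, unexplained Hy's Law cases with ALP at most 8x and TBL above 2x and up to 3x ULN:

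- AST/ALT above 5x and up to 8x, under two weeks, monitoring kept: only the Grade 3 hold applies, and ABI-009 may resume at a modified dose at Grade 1 or less with no alternative cause required.
- AST/ALT 3x to 5x, graded below Grade 3: no hold criterion is met. What remains is the discretionary hold and a recommended withdrawal at 14 days that can be overridden by agreement.

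This rests on the printed table being complete, on the grade boundaries read from 6.3.1, and on the specific liver rule governing restart where both holds apply. If the second assumption fails, the lower window falls under the Grade 3 hold and the rest stands. The share of patients affected is not given and is probably a minority. Patients with an evident alternative cause are outside the point, since they would not meet 6.2.2.1 anyway. A reader might also infer a bias in dose finding; there is none, because the Hy's Law DLT ignores baseline, so DLT counting and the MTD are unaffected.

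**What to change.** First confirm against the source file that the 6.2.2.1 table has only one row. Then:

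1. Add to 6.2.2.2: any Hy's Law case as defined in 6.2.1 that does not meet 6.2.2.1 requires ABI-009 to be withheld pending investigation, whatever the baseline, grade or symptoms. Rechallenge is allowed only under the alternative-cause condition of 6.2.2.2 and the agreement required by 6.2.2.3. This sentence alone closes both parts of the practical gap, using a definition already in the protocol.
2. Add a row to 6.2.2.1 for baseline at or above ULN, with a threshold chosen by the sponsor. Because criterion 5b admits values up to 5x with liver metastases, a fixed 3x ULN cannot serve every baseline; a multiple of baseline is needed for the higher ones, and the documents give no value for it.
3. State in 6.2.2.1 whether baseline and elevation refer to the same enzyme.
4. Correct the cross-reference in 6.2.2.3 from 6.2.1 to 6.2.2.1.

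The cost is one sentence, one table row, one clarification and one corrected reference. The downside is that a few more patients will have ABI-009 held or stopped.

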6.2.2.2. Criteria for Conditional Withholding of ABI-009 Due to Potential Hepatotoxicity

For patients who do not meet the criteria for permanent discontinuation of ABI-009 and have no underlying liver disease, and eligibility criteria requiring normal transaminases and TBL at baseline or patients with underlying liver disease and baseline abnormal transaminases, the following rules are recommended for withholding of ABI-009:

- Elevation of either AST or ALT according to the following schedule:

Baseline AST or ALT value	AST or ALT elevation
Any	> 8x ULN at any time
Any	> 5x ULN but < 8x ULN for \geq 2 weeks
Any	> 5x ULN but < 8x ULN and unable to adhere to enhanced monitoring schedule
Any	\geq 3x ULN with clinical signs or symptoms that are consistent with hepatitis (such as right upper quadrant pain/tenderness, fever, nausea, vomiting, jaundice).

- OR: TBL $>$ 3x ULN at any time
- OR: ALP $>$ 8x ULN at any time

ABI-009 should be withheld pending investigation into alternative causes of DILI. Rechallenge may be considered if an alternative cause for impaired liver tests (ALT, AST, and ALP) and/or elevated TBL is discovered and the laboratory abnormalities resolve to normal or baseline.

6.2.2.3. Criteria for Rechallenge with ABI-009 After Potential Hepatotoxicity

The decision to rechallenge the patient should be discussed and agreed upon unanimously by the patient, investigator, and AADI medical monitor.

If signs or symptoms recur with rechallenge, then ABI-009 should be permanently discontinued. Patients who clearly meet the criteria for permanent discontinuation (as described in [Section 6.2.1](#)) should never be rechallenged.

6.2.3. Overdose

On a per dose basis, an overdose is defined as 10% over the protocol-specified dose of ABI-009 assigned to a given patient, regardless of any associated AEs or sequelae.

On a schedule or frequency basis, an overdose is defined as anything more frequent than the protocol required schedule or frequency.

On an infusion rate basis, an overdose is defined as any rate faster than the protocol-specified rate of 30 minutes for each infusion.

6.3. Nivolumab Dose Modification and Stopping Rules

6.3.1. Dose Modification and Stopping Rules

Nivolumab (Opdivo®); see product information at www.accessdata.fda.gov

Withhold nivolumab for any of the following:

- Immune-mediated Grade 2 pneumonitis**

Monitor patients for signs and symptoms of pneumonitis. Administer corticosteroids at a dose of 1 to 2 mg/kg/day prednisone equivalents for Grade 2 or greater pneumonitis, followed by corticosteroid taper. Permanently discontinue nivolumab for severe (Grade 3) or life-threatening (Grade 4) pneumonitis and withhold nivolumab until resolution for moderate (Grade 2) pneumonitis

- Immune-mediated Grade 2-3 colitis**

Monitor patients for immune-mediated colitis. Administer corticosteroids at a dose of 1 to 2 mg/kg/day prednisone equivalents followed by corticosteroid taper for severe (Grade 3) or life-threatening (Grade 4) colitis. Administer corticosteroids at a dose of 0.5 to 1 mg/kg/day prednisone equivalents followed by corticosteroid taper for moderate (Grade 2) colitis of more than 5 days duration; if worsening or no improvement occurs despite initiation of corticosteroids, increase dose to 1 to 2 mg/kg/day prednisone equivalents. Withhold nivolumab for Grade 2 or 3 immune-mediated colitis. Permanently discontinue nivolumab for Grade 4 colitis or for recurrent colitis upon restarting nivolumab.

- Immune-mediated hepatitis.** Aspartate aminotransferase (AST) or alanine aminotransferase (ALT) greater than 3 and up to 5 times upper limit of normal (ULN) or total bilirubin greater than 1.5 and up to 3 times ULN

Monitor patients for abnormal liver tests prior to and periodically during treatment. Administer corticosteroids at a dose of 1 to 2 mg/kg/day prednisone equivalents for Grade 2 or greater transaminase elevations, with or without concomitant elevation in total bilirubin. Withhold nivolumab for moderate (Grade 2) and permanently discontinue nivolumab for severe (Grade 3) or life-threatening (Grade 4) immune-mediated hepatitis

- Immune-mediated nephritis and renal dysfunction. Creatinine greater than 1.5 and up to 6 times ULN or greater than 1.5 times baseline**

Monitor patients for elevated serum creatinine prior to and periodically during treatment. Administer corticosteroids at a dose of 1 to 2 mg/kg/day prednisone equivalents followed by corticosteroid taper for life-threatening (Grade 4) serum creatinine elevation and permanently discontinue nivolumab. For severe (Grade 3) or moderate (Grade 2) serum creatinine elevation, withhold nivolumab and administer corticosteroids at a dose of 0.5 to 1 mg/kg/day prednisone equivalents followed by corticosteroid taper; if worsening or no improvement occurs, increase dose of corticosteroids to 1 to 2 mg/kg/day prednisone equivalents and permanently discontinue nivolumab.

- **Immune-mediated hypothyroidism or hyperthyroidism**

There are no recommended dose modifications for hypothyroidism or hyperthyroidism.

Monitor thyroid function prior to and periodically during treatment. Administer hormone replacement therapy for hypothyroidism. Initiate medical management for control of hyperthyroidism. There are no recommended dose adjustments of nivolumab for hypothyroidism or hyperthyroidism.

- **Any other severe or Grade 3 treatment-related adverse reactions**

For any suspected immune-mediated adverse reactions, exclude other causes. Based on the severity of the adverse reaction, withhold nivolumab, administer high-dose corticosteroids, and if appropriate, initiate hormone-replacement therapy. Upon improvement to Grade 1 or less, initiate corticosteroid taper and continue to taper over at least 1 month. Consider restarting nivolumab after completion of corticosteroid taper based on the severity of the event.

6.3.2. Dosage Adjustments, Delays, Rules for Withholding or Restarting, Permanent Discontinuation

Resume nivolumab in patients whose adverse reactions recover to Grade 0-1.

Permanently discontinue nivolumab for any of the following:

- Any life-threatening or Grade 4 adverse reaction
- Grade 3 or 4 pneumonitis
- Grade 4 colitis
- AST or ALT greater than 5 times ULN or total bilirubin greater than 3 times ULN
- Creatinine greater than 6 times ULN
- Any severe or Grade 3 treatment-related adverse reaction that recurs
- Inability to reduce corticosteroid dose to 10 mg or less of prednisone or equivalent per day within 12 weeks
- Persistent Grade 2 or 3 treatment-related adverse reactions that do not recover to Grade 0-1 within 12 weeks after last dose of nivolumab

7. STUDY DRUG MANAGEMENT

7.1. Description of Study Drugs

7.1.1. ABI-009 Packaging, Labeling, and Storage

ABI-009 will be supplied by the Sponsor in single-use vials as lyophilized product. Each single-use 50-mL vial will contain 100 mg rapamycin and approximately 800 mg of human albumin as a stabilizer. Each vial will be labeled according to country-specific regulatory requirements for labeling of IPs.

Unopened vials of ABI-009 should be stored in a refrigerator (2°-8°C; 36°-46°F) in original cartons to protect from light. Reconstituted ABI-009 may be stored for up to 4 hours at 2-8°C (36°- 46°F), followed by 4 hours at room temperature (<25°C) in the IV bag. Both unopened vials of ABI-009 and reconstituted ABI-009 should be stored in an area free of environmental extremes and must be accessible only to study personnel.

Temperature records for ABI-009 must be made available to AADi or Sponsor nominated Contract Research Organization monitoring teams for verification of proper study drug storage.

